5.2.4. Prior Cancer Therapy

Patient prior cancer therapy will be tabulated by dose level and overall using all patients in the safety population. This table will include the total number of prior treatments in the advanced/metastatic setting per patient (summarized as both continuous variable and categorical variable (0, 1, 2, 3, and ≥ 4)); the treatment type of prior treatment by treatment setting; time since the last prior systemic anti-cancer therapy; the reason for discontinuation of the last prior systemic anti-cancer therapy; any prior cancer surgery (lung) (yes/no); any radiation treatment (yes/no); the number of patients with prior EGFR TKI treatment (i.e., Osimertinib or Other) and any discontinuation of EGFR TKI treatment due to disease progression. Prior cancer treatments will be listed and are coded according to the World Health Organization (WHO) Drug Dictionary (WHODrug) March 2020 DDE B3.

Time since the Last Prior Systemic Anti-Cancer Therapy (Months) is calculated as (first dosing date for pharmacokinetics assessments (i.e. C1D-16) – date of last prior systemic anti-cancer therapy + 1)/30.4375. If the month and year of the therapy are provided but the day is missing, the missing day is imputed as 15. If only the year is provided, then the missing month and day are imputed as July 1 for the calculation. If the year is missing, the patient will be excluded from the analysis.

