7.1.2. Exclusion Criteria

A patient will not be eligible for participation in this study if *any* of the following criteria apply.

- 1. Treatment with any of the following:
 - a. EGFR TKIs (erlotinib, gefitinib, afatinib, osimertinib) within 9 days of the first dose of study drug; other approved EGFR TKIs within 5 half-lives of the first dose of study drug

- b. Investigational agents within 28 days, or 5 half-lives, whichever is longer, of the first dose of study drug; antibody based therapy within 6 weeks of the first dose of study drug
- c. *Part 1:* More than 2 prior lines of cytotoxic chemotherapy for advanced NSCLC
- d. Part 2: Previous treatment with osimertinib or other T790M active EGFR TKI
- e. Part 2: Any prior cytotoxic chemotherapy for advanced NSCLC
- 2. Major surgery within 14 days of the first screening visit
- 3. Blood transfusions or hematopoietic growth factor therapy within 14 days prior of first screening visit
- 4. Prior radiotherapy treatment to > 25% of the bone marrow or radiotherapy with a wide field of radiation within 28 days of the first dose of study drug
- 5. Patients receiving medications, herbal supplements, or foods known to be potent inhibitors of CYP3A4 or orally administered sensitive substrates of CYP3A4 within 14 days prior to first dose of study drug, including but not limited to the following:
 - a. **Inhibitors**, for example: clarithromycin, diltiazem, erythromycin, grapefruit juice, itraconazole, ketoconazole, nefazodone, ritonavir, telithromycin, and verapamil
 - b. **Substrates**, for example: astemizole, cisapride, cyclosporine, dihydroergotamine, ergotamine, everolimus, pimozide, quinidine, sirolimus, and tacrolimus
- 6. Patients receiving medications, herbal supplements, or foods known to be potent inducers of CYP3A4 within 21 days prior to the first dose of study drug, including but not limited to the following:
 - a. **Inducers**, for example: carbamazepine, *Hypericum perforatum* (St. John's wort), phenobarbital, phenytoin, rifampin
- 7. Patients receiving medications, herbal supplements, or foods known to be potent inhibitors of BCRP within 14 days prior to first dose of study drug, including but not limited to the following:
 - a. **Inhibitors**, for example: sulfasalazine, curcumin, turmeric supplements, cyclosporine, eltrombopag

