4.2.1. Adverse Events (AEs)

The severity (toxicity grade) of AEs will be graded according to the National Cancer Institute (NCI) Common Terminology Criteria for Adverse Events (CTCAE), Version 4.03.

All AEs will be classified by System Organ Class (SOC) and Preferred Term (PT) according to the Medical Dictionary for Regulatory Activities (MedDRA) version 23.0.

Treatment-emergent AEs (TEAEs) are defined as any AE occurring on or after the first dose of study drug (i.e., C1D-16) until 30 days after the last dose of study drug (G1T38 or Osimertinib, which is later) but prior to the start of survival follow-up. For AEs with an incomplete or unknown/not reported onset date, the imputed onset date will be used to determine if the AE is treatment-emergent.

AEs with onset dates that are partially/completely missing will be imputed as follows:

If the start date has month and year but day is missing,

- If the month and year is the same as the first dose date, then the first dose date will be used, otherwise, the first day of the month will be used

G1 Therapeutics, Inc.
Clinical Study Protocol G1T38-03
Statistical Analysis Plan

If the start date has year, but day and month are missing,

- If the year is the same as the first dose date, then the first dose date will be used, otherwise 1st Jan will be used

If the start date of an event is completely missing, then AE start date is imputed with the first dose date.

After imputation, the imputed start date will be compared with the complete or imputed (if missing or partial) AE stop date. If the imputed start date is later than the stop date, the stop date will be used as imputed start date instead.

Imputation rules for missing or partial AE stop date are defined below:

- If the stop date has month and year but day is missing, the last day of the month will be imputed
- If the stop date has year, but day and month are missing, the 31st of December will be imputed
- If the AE end date is completely missing, the last dose date +30 days will be used as the AE end date.

After the imputation, the imputed AE stop dates will be compared against the date of death, if available. If the date is later than the date of death, the date of death will be used as the imputed date instead.

The following durations will be derived for an AE, AE leading to death, AE leading to discontinuation of any study drug as appropriate and will be displayed in the corresponding AE listings. Cycle 1 Day -16 is used for date of first dose.

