5.2.6. Prior and Concomitant Medications

Prior and concomitant medications will be coded using the WHODrug version dated March 2020 DDE B3. Prior medications include medications that were taken prior to the first dose of any study treatment. Concomitant medications during the treatment period include medications that started at any time and were taken at any time after the start of study treatment until 29 days after the end of study treatment. Post-treatment medications are those medications were started on or after the last dose of study drug (G1T38 or osimertinib, which is later) + 30 days.

Medications with incomplete start and/or end dates will be imputed for the purpose of classification of prior and concomitant according to the specifications described below. Medications with incomplete start and/or end dates will be assumed to be concomitant if it cannot be shown that the medication was not taken during the treatment period.

Imputation rules for missing or partially missing medication start/stop dates are defined below:

Missing or partially missing medication start date:

If the start date has month and year but day is missing,

G1 Therapeutics, Inc.
Clinical Study Protocol G1T38-03
Statistical Analysis Plan

- If the month and year is the same as the first dose date, then the first dose date will be used, otherwise, the first day of the month will be used

If the start date has year, but day and month are missing,

- If the year is the same as the first dose date, then the first dose date will be used, otherwise 1st Jan will be used

If the start date of an event is completely missing, then the start date will be imputed as the earlier date between

- the first dose date of study drug
- the end date of the medication (if complete date)

Any above imputed started date should be no later than the end date, if available. In case the imputed started date is later than the end date, the start date will be imputed as the end date of the medication.

Missing or partial medication stop date:

- If the stop date has month and year but day is missing, the last day of the month will be imputed
- If the stop date has year, but day and month are missing, the 31st of December will be imputed
- If the medication is not ongoing, the end date is completely missing, the end date will be imputed as the later date between:
 - the date of last study visit
 - the start date of the medication (if complete date)

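### SAP 5.2.4 imputes partial dates of last prior therapy without requiring them to precede first dose, so the time since last prior therapy can come out zero or negative

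*SAP*

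**What the plan says.** SAP 5.2.4 defines the variable, in months, as "first dosing date for pharmacokinetics assessments (i.e. C1D-16) – date of last prior systemic anti-cancer therapy + 1)/30.4375". It has three rules for incomplete dates:

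- Day missing: "If the month and year of the therapy are provided but the day is missing, the missing day is imputed as 15".
- Month and day missing: "If only the year is provided, then the missing month and day are imputed as July 1 for the calculation".
- Year missing: "If the year is missing, the patient will be excluded from the analysis".

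The first two apply whatever the date of first dose. The general missing-data section (SAP 5.1.2) adds no limit for these dates.

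Protocol 7.1.2, criterion 1a, excludes patients treated with "EGFR TKIs (erlotinib, gefitinib, afatinib, osimertinib) within 9 days of the first dose of study drug". The SAP covers Part 1 only, and the bar on previous osimertinib applies to Part 2 only.

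Two other date rules in the SAP carry an ordering check. For AE onset (SAP 4.2.1): "If the imputed start date is later than the stop date, the stop date will be used as imputed start date instead". For medications (SAP 5.2.6): "Any above imputed started date should be no later than the end date, if available".

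**The concern.** Therapy that is prior to the study cannot end after the first study dose, so a negative interval is an error and not a conservative choice. The rule produces one whenever the 15th or July 1 falls more than one day after Cycle 1 Day -16. The short TKI window makes a same-month or same-year stop an ordinary, permitted case.

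What is at stake is small but visible. SAP 5.1.1 reports mean, median, standard deviation, minimum and maximum for continuous variables, by dose level and overall. Under Protocol 6.1.1 a cohort has 3 to 6 patients. An impossible value would therefore stand as the reported minimum and pull the cohort mean. If nothing is specified, whoever programs the table must invent a rule when the value appears.

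**Working it through.** The plan gives no figure of its own to reproduce, so this is date arithmetic with the SAP 5.2.4 formula.

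**Inputs**

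- Interval in days = (Cycle 1 Day -16 date) - (date of last prior therapy) + 1; divide by 30.4375 for months (SAP 5.2.4).
- Imputed date: the 15th, or July 1 (SAP 5.2.4).
- Minimum gap for the named EGFR TKIs: 9 days (Protocol 7.1.2, criterion 1a).
- Cohort size: 3 to 6 (Protocol 6.1.1 and 6.1.1.1).
- Assumptions: the date of last therapy means its stop date; 2019 is an illustrative year.

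**Day missing, same month as first dose**

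With first dose on day d of the month, the interval is d - 15 + 1 = d - 14 days.

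- A 9-day gap within one month needs d of at least 10, or 11 if a gap of exactly 9 days counts as excluded.
- d = 10: -4 days (-0.13 months). d = 13: -1 day (-0.03 months). d = 14: 0.
- Example: TKI stopped 1 March, first dose 12 March. True value 12 - 1 + 1 = 12 days (0.39 months). SAP value 12 - 15 + 1 = -2 days (-0.07 months).

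Protocol criterion 1c limits prior chemotherapy in Part 1 by number of lines and gives no gap in days. For such therapy the arithmetic reaches -12 days (-0.39 months) with first dose on day 2.

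**Year only, same year as first dose**

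In 2019, July 1 is day 182 of the year. With first dose on day y, the interval is y - 182 + 1 = y - 181 days.

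| First dose (2019) | y | Interval, days | Months |
|---|---|---|---|
| 10 January | 10 | -171 | -5.62 |
| 15 January | 15 | -166 | -5.45 |
| 15 March | 74 | -107 | -3.52 |
| 15 April | 105 | -76 | -2.50 |
| 29 June | 180 | -1 | -0.03 |
| 30 June | 181 | 0 | 0 |

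The result is negative for first doses from 1 January to 29 June: 180 of 365 calendar dates, or 49%. With the 9-day TKI gap, the most negative value is about -5.6 months.

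**Effect on a cohort summary**

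Take a patient who stopped on 20 February 2019, has only the year recorded, and starts on 15 March 2019.

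- True value: +24 days (0.79 months). SAP value: -107 days (-3.52 months).
- Error: 24 + 107 = 131 days; 131/30.4375 = 4.30 months.
- Shift in the mean: 4.30/3 = 1.4 months with 3 values, 4.30/6 = 0.7 months with 6.
- The minimum becomes -3.52 months.

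**Effect of a cap**

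With the imputed date held at the day before first dose or earlier, the smallest possible interval is 1 + 1 = 2 days (0.066 months), so no zero or negative value remains. With the midpoint rule, the year-only example runs from 1 January (day 1) to 14 March (day 73). The midpoint is day 37, 6 February, and the interval is 74 - 37 + 1 = 38 days (1.25 months) against a true 0.79. In the day-missing example, the midpoint of 1 and 11 March is 6 March, giving 12 - 6 + 1 = 7 days (0.23 months) against a true 0.39.

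**The case against.** The strongest reply is that this hardly matters.

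- **One descriptive row.** Part 1 has no formal test, and no DLT, safety, response, PFS or PK result uses this variable. Prior treatments are also listed, so an odd value can be traced. This stands, and it sets the weight of the point.
- **The large errors need an unlikely record.** Sites must document eligibility before inclusion, and monitoring verifies the entry criteria in full. A site that confirmed a 9-day gap for a January start would have to know the stop date better than to the year. This stands as an argument for rarity. It does not exclude the case, least of all for chemotherapy, which criterion 1c does not tie to a gap in days.
- **The day-missing error is a few days for TKIs.** Such a patient is already near the bottom of the distribution, so the median would usually not move. This also stands; the mean and minimum are what can change.
- **The other SAP checks are not the same rule.** They order an imputed start against its own stop. SAP 5.2.6 also imputes medication stops to month-end or 31 December without a cap at first dose. This stands, so those checks are an analogy and do not show that the SAP contradicts itself.

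A reader might also infer that an imputed stop close to first dose would register as a washout breach. The documents do not support that. SAP 5.2.2 takes deviations from the Protocol Deviation Logs and a classification meeting, not from this interval. Nor is a small positive interval impossible: just over 9 days is about 0.3 months.

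**Conclusion.** The point holds as a minor correction. The rule as written can return an impossible value: about -4 to 0 days for a TKI when the day is missing and first dose falls on days 10 to 14, and down to about -5.6 months when only the year is known and first dose is before 30 June. The year-only case carries most of the weight.

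This rests on reading the date of last therapy as its stop date and on at least one patient having a partial date in the month or year of first dose. The documents do not give that frequency; it is probably low and may be nil.

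The consequence stops at the mean and minimum of one baseline variable in small cohorts. A reader might infer that the trial's conclusions are affected; nothing in the SAP feeds this variable into any endpoint.

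**What to change.** Add to SAP 5.2.4, before database lock: an imputed date of last prior therapy may not be later than the day before Cycle 1 Day -16. If the 15th or July 1 falls on or after Cycle 1 Day -16, use the midpoint (rounded down to a whole day) between the earliest date consistent with the recorded parts and the day before Cycle 1 Day -16. Another date in that range would also serve, provided it is fixed in advance.

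The cost is a sentence or two in the SAP and a line of code. There is a small downside: the imputed interval is still approximate and can still be shorter than the 9-day gap. The SAP should therefore add that this variable is descriptive and is not to be used to judge washout compliance.

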5.2.5. Medical History

Medical history will be coded using MedDRA Version 23.0. Medical history will be listed for all enrolled patients (SOC, PT, and verbatim term) by dose level and overall.

5.2.6. Prior and Concomitant Medications

Prior and concomitant medications will be coded using the WHODrug version dated March 2020 DDE B3. Prior medications include medications that were taken prior to the first dose of any study treatment. Concomitant medications during the treatment period include medications that started at any time and were taken at any time after the start of study treatment until 29 days after the end of study treatment. Post-treatment medications are those medications were started on or after the last dose of study drug (G1T38 or osimertinib, which is later) + 30 days.

Medications with incomplete start and/or end dates will be imputed for the purpose of classification of prior and concomitant according to the specifications described below. Medications with incomplete start and/or end dates will be assumed to be concomitant if it cannot be shown that the medication was not taken during the treatment period.

Imputation rules for missing or partially missing medication start/stop dates are defined below:

Missing or partially missing medication start date:

If the start date has month and year but day is missing,

G1 Therapeutics, Inc.
Clinical Study Protocol G1T38-03
Statistical Analysis Plan

- If the month and year is the same as the first dose date, then the first dose date will be used, otherwise, the first day of the month will be used

If the start date has year, but day and month are missing,

- If the year is the same as the first dose date, then the first dose date will be used, otherwise 1st Jan will be used

If the start date of an event is completely missing, then the start date will be imputed as the earlier date between

- the first dose date of study drug
- the end date of the medication (if complete date)

Any above imputed started date should be no later than the end date, if available. In case the imputed started date is later than the end date, the start date will be imputed as the end date of the medication.

Missing or partial medication stop date:

- If the stop date has month and year but day is missing, the last day of the month will be imputed
- If the stop date has year, but day and month are missing, the 31st of December will be imputed
- If the medication is not ongoing, the end date is completely missing, the end date will be imputed as the later date between:
 - the date of last study visit
 - the start date of the medication (if complete date)

After the imputation, the imputed dates will be compared against the date of death, if available. If the date is later than the date of death, the date of death will be used as the imputed date instead.

The number and percentage of patients taking concomitant medications during the treatment period will be summarized by anatomical therapeutic chemical (ATC) class level 4 (chemical subgroup) and PT for the safety population. Although a patient may have taken the same medication multiple times, the patient is counted only once within an ATC classification. The same patient may contribute to two or more PTs in the same classification.

All medications will be listed for enrolled patients with a flag for prior and/or concomitant, or post-treatment.

5.2.7. Treatment Duration

Study drug exposures will be summarized for the safety population using descriptive statistics.

G1 Therapeutics, Inc.
Clinical Study Protocol G1T38-03
Statistical Analysis Plan

Exposure to G1T38 and Osimertinib will be categorized in intervals (<3 Months, 3 - <6 Months, 6 - <9 Months, 9 - <12 Months, 12 - <15 Months, 15 - <18 Months, 18 - <21 Months, 21 - <24 Months, >=24 Months) and summarized by dose level and overall. Interval in Months is calculated by duration in days/30.4375.

5.2.8 Treatment Compliance

G1T38 drug compliance will be summarized using descriptive statistics. The compliance summaries will include the prescribed G1T38 duration (in months), the exposure to G1T38 (in months), and the proportion (%) of days G1T38 is taken. The proportion (%) of days G1T38 is taken will also be summarized in categories “<70%”, “≥70% - <80%”, “≥80% - <90%”, “≥90% - <100%”, and “=100%.” The number and percentage of patients with any G1T38 dose reductions will also be summarized.

Study drug compliance summaries will be based on the safety population.

A listing of exposure and compliance data containing the information described in the sections above will be provided.

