12.3.1. Other Safety Endpoints

Observed values and changes from baseline in vital signs, ECG readings, echocardiogram/MUGA scan results, and hematology, clinical chemistry, and liver function parameters will be tabulated at each visit. Toxicities for clinical labs will be characterized according to CTCAE, Version 4.03. Shifts in toxicity grades from baseline to each visit, and

from baseline to the worst grade during the study will be summarized. Summaries examining maximum and minimum post-baseline changes will consider both scheduled and unscheduled data.

Graphical presentations of safety data will be presented as is deemed appropriate. This may include, but is not restricted to, presentation of parameters against time, concentration or shift plots. For example, graphical presentations of average changes over time will provide additional focus to be placed on neutrophils and platelet data.

Dose reductions/modifications, interruptions, compliance, and patient exposure will be summarized for each study therapy component, where appropriate.

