4.2.7. Treatment Exposure and Compliance

Prescribed duration of treatment (days) is defined as the total number of days that the patient will have been prescribed study medication, that is, including days on treatment before Cycle 1 Day 1 and days on treatment from Cycle 1 Day 1 to treatment end day. Prescribed duration of G1T38 (months) is calculated as (last dose date on the dosing log – first date of continuous daily dosing (C1D1) + x + 1)/30.4375, where x is the number of days patient received G1T38 before C1D1. For example, for a patient who took one dose of G1T38 each on C1D-16 and C1D-2 respectively and took last dose on or after the first date of continuous, daily dosing of G1T38 (C1D1), Days on Treatment = Date of last dose – C1D1 date + 3; for patients who did not start continuous daily dosing, total number of days on dosing of G1T38 before C1D1 will be used as prescribed duration. Prescribed duration of Osimertinib (months) is calculated as (last dose date on the dosing log - the first date of daily osimertinib (only) dosing (i.e., C1D-14) + 1)/30.4375.

The exposure to G1T38 (months) is calculated by (prescribed G1T38 duration - days of interruption as captured in dosing log)/30.4375. Days of interruption is defined as (start date of next record – end date of current record – 1).

For subjects with last dose date is missing from dosing log, if end of treatment date is not missing, date of end of treatment will be used as last dose date. Otherwise, the later date between the last visit date during the treatment phase and last contact date will be used, but the date must be prior to the start of survival follow-up.

Compliance of G1T38 is expressed as a percentage of days G1T38 was actually taken during the treatment phase and will be calculated as exposure to G1T38 divided by prescribed G1T38 duration multiplied by 100.

Dose reduction will be flagged when a total daily dose recorded in G1T38 dosing log is less than the previous entry. Patient with dose interval change but total daily dose unchanged (e.g. 300 mg QD vs 150 mg BID) will not be considered as dose reduction.

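### The SAP defines net exposure, compliance and dose-reduction summaries for G1T38 only, although the protocol plans them for each component, and Section 7 does not record the departure

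*SAP*

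**What the plan says.** Protocol 12.3.1, which covers Part 1, states: "Dose reductions/modifications, interruptions, compliance, and patient exposure will be summarized for each study therapy component, where appropriate". There are two components, G1T38 and osimertinib.

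SAP 4.2.7 treats them differently.

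- G1T38 exposure is net of off-drug days: "The exposure to G1T38 (months) is calculated by (prescribed G1T38 duration - days of interruption as captured in dosing log)/30.4375".
- G1T38 also has a compliance measure ("Compliance of G1T38 is expressed as a percentage of days G1T38 was actually taken during the treatment phase") and a reduction flag ("Dose reduction will be flagged when a total daily dose recorded in G1T38 dosing log is less than the previous entry").
- Osimertinib has one derivation, a span of dates: "Prescribed duration of Osimertinib (months) is calculated as (last dose date on the dosing log - the first date of daily osimertinib (only) dosing", the start being Cycle 1 Day -14. Nothing is subtracted for interruptions, and no osimertinib exposure, compliance or reduction variable is defined.

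SAP 5.2.7 nevertheless puts both drugs in one table: "Exposure to G1T38 and Osimertinib will be categorized in intervals". SAP 5.2.8 then summarises compliance and dose reductions for G1T38 only: "G1T38 drug compliance will be summarized using descriptive statistics". In SAP 5.2.10, adverse events leading to dose reduction are tabulated for G1T38 only.

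**The concern.** The protocol expects osimertinib to be held and reduced. Table 8-2 provides for holds of up to 3 weeks with resumption at 80 or 40 mg. Section 8.3.3.2.2 provides for a hold and a lower restart dose after QTc prolongation. Appendix 6 advises study drug washouts around brain and thoracic radiotherapy. Section 8.11 has sites keep pill counts for both drugs.

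A primary objective of Part 1 is the safety and tolerability of the two drugs given together. If the SAP is followed as written, no planned exposure, compliance or reduction summary will show an osimertinib hold or a reduction to 40 mg. One table will also carry the word exposure for two different quantities: G1T38 without off-drug days and osimertinib with them. SAP Section 7 lists departures as small as renaming the clinical benefit rate, but not this one.

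**Working it through.** Most of the check is a comparison of texts.

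| Item in Protocol 12.3.1 | G1T38 in SAP | Osimertinib in SAP |
|---|---|---|
| Exposure | Net of interruption days (4.2.7), tabulated (5.2.7) | Date span only (4.2.7), tabulated as exposure (5.2.7) |
| Interruptions | Derived (4.2.7) | Not derived |
| Compliance | Derived (4.2.7), summarised (5.2.8) | Neither |
| Dose reductions | Flagged (4.2.7), summarised (5.2.8); adverse events leading to reduction (5.2.10) | None |

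**The SAP's own example.** For G1T38, duration in days is last dose date − C1D1 date + x + 1, where x is the number of G1T38 dosing days before C1D1. With doses on Days -16 and -2, x = 2, so the constant is 2 + 1 = 3, as the SAP states. The G1T38 formula thus already leaves out the lead-in days without a G1T38 dose.

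**Illustration for osimertinib.** The documents give no osimertinib hold data, so the hold is an assumption: one hold of h = 21 days, the 3 weeks in Table 8-2. Let D be the gross duration in days.

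- Gross months = D / 30.4375
- Net months, by the G1T38 rule = (D − h) / 30.4375
- Relative excess of gross over net = h / (D − h)
- Compliance = (D − h) / D

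| Gross months | D (days) | Net months | Excess | Compliance |
|---|---|---|---|---|
| 3.00 | 91.31 | 2.31 | 21/70.31 = 29.9% | 77.0% |
| 6.00 | 182.63 | 5.31 | 21/161.63 = 13.0% | 88.5% |
| 12.00 | 365.25 | 11.31 | 21/344.25 = 6.1% | 94.3% |

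The absolute excess is 21/30.4375 = 0.69 months in each row. At 6 gross months, total holds of 7 to 42 days give 7/175.63 = 4.0% to 42/140.63 = 29.9%. With no hold the excess is zero.

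**Effect on the 3-month categories in SAP 5.2.7.** A 21-day hold moves a patient down a category only if the gross duration lies less than 0.69 months above a category boundary. That is 0.69/3 = 23% of the width of a 3-month category. For example, 168 gross days against 147 net is 5.52 against 4.83 months, and both fall in the 3 to <6 month category. The continuous summaries would move in every case with a hold.

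**Dose reduction.** A change from 80 to 40 mg leaves D unchanged. A patient on 80 mg for half the time and 40 mg for the other half takes 0.5 × 1 + 0.5 × 0.5 = 75% of the full dose, with no change in duration-based exposure. Only a reduction flag would show it, and the SAP has none for osimertinib.

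**The case against.** Several points on the other side have force.

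- **The protocol sentence is qualified.** It ends with a proviso that leaves discretion. That stands, but the SAP gives no reason for using it, and the protocol itself provides for osimertinib holds and reductions.
- **Much of osimertinib tolerability is reported.** A reader might infer that combination tolerability is only half reported. The documents do not support that. SAP 5.2.10 tabulates osimertinib-related events, including serious and Grade 3 or higher ones, and events leading to osimertinib discontinuation. It also lists the action taken for each event, in a study part of at most 36 patients.
- **Frequent holds would often leave a trace.** A reader might infer that a dose level with many osimertinib holds would look as tolerable as one without. That does not follow. Protocol 8.3.3.2 interrupts osimertinib for Grade 3 or higher toxicity, and such events, when attributed to osimertinib, enter the Grade 3 or higher tables. For hematologic toxicity or diarrhea that may be due to either drug, G1T38 is reduced first, and that enters the G1T38 reduction summary. What can escape the Grade 3 or higher tables is a hold or reduction for lower-grade unacceptable toxicity, or a radiotherapy washout. Discontinuation tables also miss patients who stay on osimertinib after a hold or at a lower dose.
- **The recommended Phase 2 dose.** A reader might infer that its choice is affected. Under the protocol the safety monitoring committee makes that choice from cumulative safety and PK data, and the SAP supports the study report. Nothing shows that the choice rests on these tables.
- **Overstatement is conditional.** A reader might infer that osimertinib exposure is overstated throughout. The SAP gives no osimertinib exposure formula. If the prescribed duration is used, only patients with a hold are affected.

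**Conclusion.** The departure from Protocol 12.3.1 is real and undeclared, and it is limited in scope. It concerns osimertinib interruptions, net exposure, compliance, dose reductions and the events leading to reduction or interruption. These would be visible only in listings, which are not the summaries that the protocol planned.

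The percentages of about 30, 13 and 6 rest on two assumptions: that SAP 5.2.7 will use the prescribed duration, the only osimertinib quantity defined, and that a patient has one 21-day hold. How many patients had a hold, and for how long, cannot be learned from the documents, so no figure for the trial can be given. Part 1 is descriptive, so no test or error rate is involved. This is a worthwhile reporting correction and does not threaten the study's main conclusions.

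**What to change.** In SAP 4.2.7, 5.2.7 and 5.2.8, apply the G1T38 derivations to the osimertinib dosing log: interruption days, exposure net of interruptions, compliance and the dose-reduction flag. In SAP 5.2.10, add adverse events leading to osimertinib dose reduction and adverse events leading to osimertinib interruption.

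The SAP already takes the last osimertinib dose date from a dosing log. Whether that log also records interruptions and dose changes cannot be seen from the documents. If it does not, label the osimertinib figure in 5.2.7 as duration including off-drug days, and declare the departure with its reason in Section 7.

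The cost is a few extra table rows and some programming.
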